3.10 Criteria for withdrawal

Every reasonable effort should be made to conduct all protocol-required procedures to complete the study. Patients may be removed from the study for the following reasons:

1. Screen Failures.
2. Withdrawal by Patient.
3. Adverse Event: Patient experiences an AE that, in the Investigator's opinion, necessitates withdrawal from the study.
4. Investigator Decision: Investigator feels it is in the patient's best interest to terminate participation for reasons other than an AE.
5. Protocol Violation: Patient is noncompliant with protocol procedures, becomes pregnant, violates study entry criteria, or starts an exclusionary concomitant medication.
6. Lost to Follow-Up: Patient fails to return for study visits and cannot be reached with reasonable, repeated attempts.
7. Administrative Reasons: The FDA or other regulatory authority discontinues the study protocol or the clinical study site discontinues participation.

Any withdrawal must be fully documented in the patient's source records. The documentation must include the reason for the withdrawal and details of any sequelae (followed until symptoms resolve or improve, as appropriate).

If a patient is withdrawn from the study, will be encouraged to complete the procedures outlined in Visits 15 and 16.

3.10.1 Screen failures

Screening failures are patients who do not fulfill the eligibility criteria for the study, and therefore must not be randomized. These patients should have the reason for study withdrawal recorded as "Eligibility Criteria not fulfilled" (i.e., patient does not meet the

required inclusion/exclusion criteria). This reason for study withdrawal is only valid for screen failures (not randomized patients).

If a patient was classified as a screen failure, dependent upon the reason for failure (e.g., low hematocrit, low T4, etc.), the patient may be rescreened one time only for study inclusion as long as rescreening takes place at least 3 months after the original Screening visit. All patients who rescreen will be assigned a new enrollment number.

3.10.2 Withdrawal of the informed consent

Patients are free to withdraw from the study at any time (IP and assessments), without prejudice to further treatment.

A patient who withdraws consent will always be asked about the reason(s) and the presence of any AEs. The Investigator will follow up AEs outside of the clinical study.

If a patient withdraws from participation in the study then his/her enrollment/randomization code cannot be reused.

3.11 Discontinuation of the study

The study may be stopped if, in the judgment of the Investigator, trial patients are placed at undue risk because of clinically significant findings that:

- meet individual stopping criteria or are otherwise considered significant
- are assessed as causally related to IP
- are not considered to be consistent with continuation of the study.

Regardless of the reason for termination, all data available for the patient at the time of discontinuation of follow-up must be recorded in the patient's source records. All reasons for discontinuation of treatment must be documented.

In terminating the study, the Investigator will ensure that adequate consideration is given to the protection of the patients' interests.

4. STUDY PLAN AND TIMING OF PROCEDURES

[Table 1](#) presents the schedule of assessments for this study.

Table 1 Study Plan

Evaluation	Screening	Run-in	Treatment Period					End of treatment/Early Termination or Rescue ^a
			1	2	3	4	5	
Visit	1	2	3	4	5	6	7	8
Week	-2	-1	0	4	8	12	15	16
Relative to Randomization (days)	-14	-9	R	28	56	84	103	112
Visit Window (±days)	(+7)	(±4^b)	0	(±5)	(±5)	(±5)	(±5)	(±4^b)
Obtain Informed Consent	X							
Review Medical and Surgical History	X							
Review Eligibility Criteria (Inclusion/Exclusion Criteria)	X							
Review Randomization Criteria			X					
Verify Patient Fasted 10 Hours	X	X	X	X	X	X	X	X
Complete Physical Examination	X							X
Brief Physical Assessment (at the Investigator's discretion)				X	X	X	X	
Body Weight	X		X	X	X	X	X	X
Height	X							
Body Mass Index	X							X
Vital signs (reclining/standing BP and HR)	X		X	X	X	X	X	X
Waist and Hip Circumference	X		X	X	X	X		X
12-lead ECG	X							X
Review Concomitant Medications ^c	X	X	X	X	X	X	X	X
Provide Diet and Exercise Counseling	X		X		X			
Verify IP Compliance				X	X	X	X	X
Dispense Study Medication			X	X	X	X		
Provide Glucose Meter and Supplies/Instructions for 7-point SMBG		X						
Perform 7-point SMBG Prior to Site Visit			X ^d	X	X	X	X ^d	X

Evaluation	Screening	Run-in	Treatment Period					End of treatment/Early Termination or Rescue ^a
	1	2	3	4	5	6	7	8
Visit	-2	-1	0	4	8	12	15	16
Week	-14	-9	R	28	56	84	103	112
Relative to Randomization (days)	(+7)	(±4 ^b)	0	(±5)	(±5)	(±5)	(±5)	(±4 ^b)
Review 7-point SMBG and hypoglycemia episodes			X	X	X	X	X	X
Collect Glucose Meter/Unused Supplies								X
Collect unused study medication								X
Dispense Rescue Medication (if needed)					X	X	X	
Assess AEs		X	X	X	X	X	X	X
Pregnancy Test (urine and serum if urine test positive) WOCBP only	X	X	X	X	X	X	X	X
Clinical Chemistry, Hematology ^c	X				X			X
eGFR and Serum Creatinine	X	x	x	x	X	x	x	X
HbA1C	X	X		X	X	X	X	X
FPG/ketones	X	X	X	X	X	X	X	X
Fasting Serum Lipids ^f	X	X			X		X	X
Thyroid function (TSH and T4)	X							
FFA	X							X
Urinalysis ^e	X							X
Double Tracer OGTT ^h with IC		X						X
Glucose Turnover Study ⁱ			X				(X) ^j	
DEXA	X							X

Abbreviations: AE adverse event, β -hCG beta subunit of human chorionic gonadotropin, BP blood pressure, CrCl creatinine clearance, DEXA Dual Energy X-ray Absorption, ECG electrocardiogram, FFA free fatty acids, FPG fasting plasma glucose, GIP glucose-dependent insulinotropic polypeptide, GLP-1 glucagon-like peptide-1, HbA1c hemoglobin A1c, HDL high-density lipoprotein, HR heart rate, IgM immunoglobulin M, IP investigational product, LDL low-density lipoprotein, OGTT oral glucose tolerance test, R randomization, SMBG self-monitored blood glucose profile, T4 thyroxine, TSH thyroid stimulating hormone, WOCBP women of childbearing potential, IC = indirect calorimetry.

- ^a Early Termination procedures are to be completed for all patients who terminate the study or are rescued before Visit 8 (Week 16) of the Treatment Period. Discontinued patients should return to the study site and complete a glucose turnover study and all assessments required for Visit 8 (Week 16) 3 to 5 days later.
- ^b The glucose turnover study at Visit 3 should take place 5 to 14 days after OGTT at Visit 2. The Visit 7 glucose turnover study should take place approximately 10 days prior to OGTT at Visit 8.
- ^c Review of concomitant medications includes over the counter drugs and herbal/nutritional therapies.
- ^d 7-point SMBG should not be performed the day immediately before clinic visit 3 and 7.
- ^e Details for safety laboratory variables are shown in [Table 5](#).
- ^f Serum lipids include total-cholesterol, LDL-cholesterol, HDL-cholesterol, non-HDL cholesterol, and triglycerides.
- ^g Hepatitis panel includes hepatitis B viral antibody IgM, hepatitis B surface antigen, and hepatitis C virus antibody.
- ^h The double tracer OGTT will include blood draws for plasma glucose, plasma insulin, plasma C-peptide, plasma glucagon, plasma GLP-1, plasma GIP, plasma ³H-glucose, ¹⁴C-glucose specific activities (until Time 300 minutes) and urine will be collected.
- ⁱ The glucose turnover test will include blood draws for glucose, insulin, C-peptide, glucagon, cortisol, growth hormone, adrenaline, and noradrenaline; and ³H-glucose specific activities (until Time 300 minutes); and urine will be collected. Glucose turnover tests will include administration of IP at Time 0.
- ^j Patients who are receiving rescue therapy or are early terminating: glucose turnover study will be performed 5 to 14 days prior to OGTT and Visit 8 assessments will also be completed prior to rescue. Glucose turnover study and Visit 8 procedures will be performed again at end of treatment for rescued patients.

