4.2 Treatment Period

After the Randomization visit (Visit 3), patients will complete study visits at 1- to 4-week intervals according to the Study Plan (Table 1) until the end of the randomized treatment period (Visit 8, Week 16). During Weeks 6 to 16 of the double-blind treatment period of the trial, patients may be eligible for the addition of open-label rescue medication to their blinded treatment regimen in order to treat ongoing hyperglycemia, based upon established laboratory FPG values and repeat, confirmatory FPG criteria (Table 2).

Table 2 Criteria for Initiation of Rescue Therapy During the Randomized Treatment Period

Visit Period	Central Laboratory FPG
Week 6	FPG >270 mg/dL (15.0 mmol/L)
After Week 6 to Week 12 (excluding Week 12)	FPG >240 mg/dL (13.3 mmol/L)
After Week 12 to Week 16 (excluding Week 16)	FPG >200 mg/dL (11.1 mmol/L)

Abbreviation: FPG fasting plasma glucose.

Patients with a laboratory FPG value meeting the lack of glycemic control criterion at a pre-specified visit will be scheduled for a Follow-up Visit (within 3 to 5 days) to obtain a second laboratory FPG value and review the patient's glucose meter readings. If the repeat laboratory FPG value still meets the criterion, the patient must be rescued. Patients should continue receiving study medication while receiving rescue therapy. Patients who meet rescue criteria in the double-blind treatment period must first complete an OGTT and the Visit 8/End of Treatment procedures, including a glucose turnover study and DEXA scan, before receiving open-label rescue medication, to ensure that important trial endpoint measurements are collected. Rescued patients will be given open-label antidiabetic rescue medication in accordance with the approved product label in the applicable country at the discretion of the Investigator, in addition to their double-blinded study medication. Rescued patients will then continue in the double-blind treatment period according to their original visit schedule.

Following initiation of open-label rescue medication, rescued patients should have their glycemic response to the rescue medication evaluated by the Investigator. At the end of the study or at early termination, rescued patients should undergo a double tracer OGTT, glucose turnover study, and DEXA scan.

4.2.1 Treatment Period visits (Visits 4 to 7, Weeks 4, 8, 12, and 15)

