7.7.2 Rescue therapy

Patients must first complete a glucose turnover study and all Week 16 visit procedures, including OGTT, before receiving open-label rescue therapy. Patients who require rescue therapy (i.e., FPG rescue criteria met) should receive standard of care treatment; however, Bydureon 2 mg subcutaneously is highly suggested. Patients should continue receiving study medication while receiving rescue therapy. Bydureon will be provided by the Sponsor.

If rescue therapy fails, further therapy will be given at the discretion of the Investigator.

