8.5 Methods for statistical analyses

Continuous variables will be presented with mean, median, 25th percentile, 75th percentile, standard deviation, minimum, maximum, and (if appropriate) the number of nonmissing observations. Categorical data will be displayed via absolute and relative frequencies for each category, including a category labeled as ‘missing’ when appropriate. The ‘missing’ category will not contribute to the denominators of relative frequencies.

All analyses will be done using values prior to rescue/intensification of treatment. Values collected after this time will be excluded from analyses. Sensitivity analyses may be conducted using all available data and including a time varying covariate that indicates rescue status.

The primary endpoint (EGP) will be tested for saxagliptin 5 mg/dapagliflozin 10 mg versus dapagliflozin 10 mg groups at the $\alpha=0.05$ level (2-sided). Other comparisons (contrasts) will be tested in an exploratory fashion at the $\alpha=0.05$ (2-sided) level. Therefore, no multiplicity control is required.

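### After a confirmed rescue FPG, rescue drug waits 5 to 14 days for two tracer tests, with no written exception for symptomatic hyperglycemia or ketosis

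*Combined protocol and SAP*

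**What the plan says.** Section 4.2 sets the rescue pathway. A patient whose laboratory FPG exceeds the Table 2 limit "will be scheduled for a Follow-up Visit (within 3 to 5 days) to obtain a second laboratory FPG value". Confirmation makes rescue mandatory: "If the repeat laboratory FPG value still meets the criterion, the patient must be rescued". The same section then says that such patients "must first complete an OGTT and the Visit 8/End of Treatment procedures, including a glucose turnover study and DEXA scan" before the open-label drug is given. Its stated reason is to secure the endpoint measurements. Section 7.7.2 repeats the rule: "Patients must first complete a glucose turnover study and all Week 16 visit procedures, including OGTT, before receiving open-label rescue therapy".

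The order and spacing of the two tests come from Table 1 footnote j: "glucose turnover study will be performed 5 to 14 days prior to OGTT and Visit 8 assessments will also be completed prior to rescue". Footnote a, in a sentence on discontinued patients, has them return and "complete a glucose turnover study and all assessments required for Visit 8 (Week 16) 3 to 5 days later".

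Rescue is meant to be added to blinded treatment: "Patients should continue receiving study medication while receiving rescue therapy". On the analysis side, section 8.5 states: "All analyses will be done using values prior to rescue/intensification of treatment". Section 8.5.1 removes rescued patients from the primary analysis.

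**The concern.** The plan declares that a patient must be rescued and then withholds the drug until a research sequence is finished. That patient already has two fasting values above a limit of 200 to 270 mg/dL, depending on the week. In the double-placebo arm, the only active treatment during the wait is the background therapy that was insufficient at entry. On both test mornings even that is delayed (3.8, 5.1.8), and the OGTT adds a 75 g glucose load (5.1.9). Section 1.3.3 itself warns of ketoacidosis with dapagliflozin, and treatment is blinded.

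For a patient without symptoms, a short wait to secure endpoint data is a defensible trade. For a patient with hyperglycemic symptoms or significant ketosis it is harder to defend, and the rescue text does not separate the two. An investigator who wants to give rescue drug early while keeping the patient on blinded treatment, as 4.2 intends, finds no sentence that permits it.

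**Working it through.** The plan states no total delay, so there is no figure to reproduce. The check adds the stated intervals and then looks for an exception.

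**Inputs**
- First qualifying FPG to repeat FPG: 3 to 5 days (4.2).
- Turnover study to OGTT in rescued patients: 5 to 14 days (footnote j).
- Nominal days: Visit 5 = 56, Visit 7 = 103, Visit 8 = 112 (Table 1).
- Assumption: the turnover study is done on the day of the repeat FPG. Any lag adds to the totals.

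**Delay as written**
- After confirmation: 5 to 14 days.
- From the first qualifying FPG: 3 + 5 = 8 to 5 + 14 = 19 days.
- Example, first qualifying FPG at Week 8: rescue on day 56 + 8 = 64 to day 56 + 19 = 75.

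**Visit 7**
The turnover study is already scheduled for day 103. If it counts as the pre-rescue study, the OGTT falls on day 103 + 5 = 108 to 103 + 14 = 117. The repeat FPG falls on day 103 + 3 = 106 to 103 + 5 = 108. The wait after the repeat is then 108 − 108 = 0 to 117 − 106 = 11 days. On the nominal schedule the OGTT comes 112 − 103 = 9 days after the turnover study.

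**Saving from a gap of 3 to 5 days**
The site can already choose any day from 5 to 14, so the two ranges are compared end against opposite end.
- Smallest: 5 − 5 = 0 days.
- Largest: 14 − 3 = 11 days. If the new gap is exactly 5 days, the largest saving is 14 − 5 = 9.
- New total from the first qualifying FPG: 3 + 3 = 6 to 5 + 5 = 10 days.

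A lag before the turnover study adds equally to both schedules and cancels in the saving.

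**Search for an exception**
- 1.3.3: positive urine ketones lead to electrolytes, bicarbonate and anion gap. Rescue timing is not mentioned.
- 3.9 and 3.9.1: the investigator may stop study drug, and ketoacidosis may lead to discontinuation. Neither gives earlier rescue on blinded treatment.
- 4.2: investigator discretion appears in the sentence on giving the rescue medication, after the pre-rescue rule. It does not waive the tests.
- 7.7: other antihyperglycemic drugs are restricted when used for more than 14 days. This might be read to allow short bridging treatment, but the section does not say so.
- 7.7.3: allows medication other than that already described. Rescue therapy is described just before it, in 7.7.2.

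None of these waives or shortens the sequence.

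**The case against.** The strongest reply is that collecting endpoints before rescue is deliberate and that the plan is not without safeguards. Ketosis has its own pathway in 1.3.3 and 3.9.1, separate from FPG-based rescue. The 14-day wording in 7.7 matches the upper end of the test gap, and 7.7.3 allows medication needed for safety. A reader might infer that the investigator is forced either to breach the sequence or to stop study drug. The documents do not support that, because 7.7 and 7.7.3 arguably leave room for short-term treatment. What stands is that neither is written as an exception to a rule stated in 4.2 and again in 7.7.2.

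Four further points are fair and limit the claim.
- A bare positive-ketone trigger would bypass the graded work-up in 1.3.3. Ketones are also a planned outcome, so changes in them are expected. The trigger should be clinically significant ketosis.
- It is tempting to call 3 to 5 days an established precedent. Footnote a does not say what the 3 to 5 days are counted from, and footnote j gives 5 to 14 days for early terminators as well. The footnotes conflict for those patients.
- Few patients are likely to be affected. Table 1 has no Week 6 visit, and Table 2 leaves Week 12 itself outside both later rows, although Table 1 marks rescue dispensing at Visits 5, 6 and 7. The 10% allowance is 0.10 × 21 = 2.1 patients per primary arm, for termination, rescue and missing assessments together.
- Skipped tests would lose data for secondary endpoints and for the optional sensitivity analysis in 8.5.4.

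**Conclusion.** The point holds as a safety gap in a stated rule. After confirmation, rescue drug waits 5 to 14 days (8 to 19 days from the first qualifying FPG), and no exception is written for symptomatic hyperglycemia or ketosis. These figures assume that the turnover study is done on the day of the repeat FPG. They do not describe every rescued patient: one who first qualifies at Visit 7 may wait about 0 to 11 days after the repeat.

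Two stronger inferences should be resisted. The sequence does not threaten the primary analysis, because 8.5.1 excludes rescued patients whether or not the tests are done. Shortening the gap does not guarantee earlier rescue either, since a site may already book the OGTT on day 5.

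The exception matters most, and the shorter gap is a secondary scheduling change. This is an inexpensive improvement worth considering. How many patients it would reach cannot be estimated from the documents beyond the pooled 10% allowance.

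**What to change.** 1. In footnote j, 4.2 and 7.7.2, state that rescue starts at once, skipping any outstanding pre-rescue test, if the patient has hyperglycemic symptoms, or ketosis that the investigator judges clinically significant after the 1.3.3 work-up (bicarbonate, anion gap). Blinded study drug continues unless 3.9 applies.
2. For other rescued patients, do the turnover study as soon as the repeat FPG is known and the OGTT no more than about 5 days later, with rescue directly afterwards.
3. Align footnotes a and j, so that early terminators have one interval with a stated starting point.

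The cost is wording in one table and two sections, tighter scheduling of two tracer days, and an occasional missing pre-rescue test in the worst-controlled patients. That loss falls on secondary endpoints and the optional sensitivity analysis. Separately, 8.5.2 does not say how a pre-rescue OGTT enters the secondary analyses, and one added sentence would settle it.

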4.1 Enrollment/Screening Period

Procedures will be performed according to the Study Plan (Table 1). Patients will be instructed to arrive in the morning for each scheduled visit. Prior to each study visit, including the Screening Visit, patients are to have fasted overnight for at least 10 hours (no food or beverage, except water). Patients are to refrain from alcohol intake and intense exercise 24 hours prior to each visit and recommend not to use tobacco/nicotine within 12 hours prior to each visit. Patients should delay administering their morning dose of metformin or metformin/sulfonylurea on the morning of the Run-in visit (Visit 2) and metformin or metformin/sulfonylurea and study medication on the morning of the study site visits during Treatment Period.

4.1.1 Screening Visit (Visit 1, Week -2)

At Screening, informed consent will be obtained prior to performing any protocol-required procedures. Patients will be assessed to ensure that they meet eligibility criteria. Patients who do not meet these criteria must not be enrolled in the study.

Screening procedures should be scheduled for at least 1 day later than the day of informed consent signature if the patient is not in a fasting state on the consent date.

The following will be performed during this visit:

- The patient's complete medical and surgical history will be recorded.
- Inclusion and exclusion criteria will be verified.
- A complete physical exam will be conducted.
- Body weight and height will be measured.
- BMI will be calculated.
- Vital signs (reclining and standing systolic and diastolic BP and heart rate [HR]) will be measured.
- Waist and hip circumference will be measured.
- 12-lead ECG will be performed.
- All prior medications (prescription medications within 3 months) and concomitant medications (including over the counter and herbal/nutritional supplements) will be reviewed.
- Diet and exercise counselling will be provided.
- Urinary pregnancy test for all female patients (WOCBP only) will be performed.
- Blood samples will be collected for the following assessments:
 - Chemistry and hematology
 - Serum creatinine (estimated GFR)
 - HbA1c
 - Fasting plasma glucose (FPG) and ketones

- Fasting serum lipid concentrations (total cholesterol, low-density lipoprotein [LDL] cholesterol, high-density lipoprotein [HDL] cholesterol, non-HDL cholesterol, and triglycerides)
- Thyroid function (TSH and T4)
- FFA
- Serum pregnancy test for all female patients (WOCBP only) if urine pregnancy test result is positive
- Urine will be collected for urinalysis.
- DEXA scan will be performed.

Individuals will be screen failed if results of any laboratory test are abnormal and clinically significant as judged by the Investigator or medical monitor. Individuals may qualify for study run-in following an acceptable repeated lab result for an initially abnormal result as judged by the Investigator).

4.1.1.1 Rescreening

If a patient was classified as a screen failure, dependent upon the reason for failure (i.e., low hematocrit, low T4, etc.), the patient may be rescreened for study inclusion as long as rescreening takes place at least 2 weeks after the original screening visit. All patients who rescreen will be assigned a new enrollment number. If a patient will be rescreened, they must continue to meet all inclusion/exclusion criteria. They must repeat all study procedures for Visit 1 at the rescreening visit. Only 1 rescreening per patient is permitted. If the patient does not meet all study requirements at the rescreening visit, the patient should be considered a screen failure.

